## XI. Data Analysis

**XI.1** *Describe the analysis methods you will use, including, if applicable, the variables you will analyze*

The main statistical analyses will be for the three-group randomized clinical trial with the primary analyses restricted to participants that do not relapse to smoking.

Participants who discontinue study participation will be assumed to have relapsed to smoking. Therefore, analyses will be restricted to those with available data.

The primary efficacy endpoints are BP and body weight. Since the aim is to evaluate long-term efficacy, the primary analysis will evaluate treatment effects at 1-year. Analyses will also be conducted to assess changes in BP and body weight at six months. The primary analysis will be restricted to participants that have not relapsed to smoking and who provide follow-up data. Secondary analysis will be performed using all

participants. The primary analysis will be performed using ANCOVA to assess for treatment effects adjusting for the baseline value of the dependent variable, study site, and any baseline variables found to differ significantly between groups. In all cases, each of the two experimental groups will be compared to the UL group. Since there are two pair-wise treatment comparisons of interest (BPC vs. UL; WGP vs. UL), we will utilize Fisher's least significant difference (LSD) approach to protect against inflation of the experimentwise error rate. An initial omnibus test will be used to test the null hypotheses that all group means are equal. Rejection of the null hypothesis will result in subsequent pair-wise comparisons between treatment groups. Conversely, if the null hypothesis associated with the omnibus test is not rejected, pair-wise comparisons will not be necessary.

Secondary endpoints will include servings of fruits and vegetables per day, dietary fat intake (% of total energy from fat), overnight urinary chloride excretion (mmol/day), and self-reported physical activity (kcal/kg/day). The analyses for the secondary endpoints will be similar to that for the primary endpoints, with groups compared using ANCOVA to assess for treatment effects adjusting for baseline values, study site, and baseline variables found to differ significantly between groups. In all cases, each of the two experimental groups will be compared to the UL group.

Relapse to tobacco use will be analyzed as an exploratory endpoint. At every contact following randomization subjects will be assessed for relapse to tobacco use, with relapse defined as using tobacco on seven consecutive days or using tobacco at least one day per week on two consecutive weeks. This definition is consistent with that proposed by the Society for Research on Nicotine and Tobacco (Hughes et al., 2003). For subjects that relapse, the date of relapse will be defined as the first day of tobacco use in the 7-day or 2-week period. Subjects that discontinue study participation prior to the 1-year follow-up visit, who have not already met relapse criteria, will be assumed to have relapsed to using tobacco. For these subjects, the date of relapse will be assigned as the day following their last study visit. Time to relapse will be analyzed using Cox proportional hazards regression (PROC PHREG) with time to relapse as the dependent variable and intervention group as the independent variable. For subjects that do not relapse to using tobacco, the time to relapse will be censored as of the date of their 1-year follow-up visit. Additional multivariable analyses assessing characteristics associated with relapse to tobacco use will be considered. However these analyses will be considered exploratory in nature since our ability to perform meaningful multivariable analyses will be dependent on the number of subjects that relapse to tobacco use.

A number of additional analyses will be performed to describe the study characteristics and assess comparability between study groups. Participant adherence will be assessed as percentage of contacts completed and compared between groups using the rank sum test. The percentage of subjects that use other products (or programs) for smoking cessation, blood pressure or weight control will be summarized separately and compared between intervention groups using Fisher's exact test. Changes in hypertension status will be noted and coded as: -1=decrease in status, 0=no change, +1=increase in status; and changes in hypertension medication status will be noted and coded as: -1=decrease in medication, 0=no change, +1=increase in medication. Using these coded variables, changes in hypertension status and medication status will be compared across treatment groups using the Kruskal-Wallis test.

Analyses for phase 1 (smoking cessation)

Although the primary analyses are for the randomized trial, the first phase of this investigation (open-label smoking cessation phase) will provide meaningful data regarding smoking cessation efforts for individuals. For this phase, the primary outcome will be prolonged tobacco abstinence at the final program session (session 4) defined as self-reported abstinence from all tobacco (not even a puff) for the last 14 days, confirmed by expired CO<10 ppm. The percentage of participants that discontinue the program prior to the 4th session will be summarized along with the reason for discontinuation. The overall abstinence rate at the end of the program will be summarized using a point estimate and 95% confidence interval, with subjects that discontinue study participation assumed to be smoking. In addition, logistic regression will be used to perform exploratory analyses to assess potential participant characteristics associated with abstinence at the end of treatment. Participant characteristics considered in this analysis will include: age (years), gender, smoking rate (cpd), and level of nicotine dependence (FTND).

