**DESCRIBE:**

- **What subjects will be asked to do/what happens in the study (in sequential order)**
- **The time period over which procedures will occur**
- **The time commitment for the subject for individual visits/procedures**
- **Long-term followup and how it occurs**

Below is a description of the study procedures. Please also see the attached Study Timeline and Flowchart.

Participants will be 500 cigarette smokers with elevated Blood Pressure (BP) who smoke at least five cigarettes per day. Patients will be eligible if their BP is in the Prehypertensive (120-139/80-89 mm Hg) or Stage I hypertensive (140-159/90-99 mm Hg) range based on JNC 7 criteria (Chobanian et al., 2003). However, we will exclude patients who are Stage II hypertensive (> 160/100 mm Hg). We will include patients who are using antihypertensive medications, provided their BP is not out of control (i.e., > 160/100 mm Hg), but will record medication, dose, and frequency so that these can potentially be adjusted for in the analyses. Participants will be instructed to continue to have their blood pressure managed under the care of their primary care provider. Participants must give the study team permission to access their medical records. This information will be used to help the study team determine whether the study is appropriate for the participant, and/or to monitor the participants medical status as needed during the course of the study.

- We also will enroll former smokers who recently quit smoking on their own. Former smokers will be eligible if they have quit smoking in the past two to six weeks. Participants who enroll in the study who are already abstinent will not take part in the smoking cessation portion of the intervention (described below).

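### The exploratory relapse comparison adjusts for nothing, not even study site; a short fixed covariate list would recover a little power at almost no cost

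*Protocol*

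**What the plan says.** Protocol XI.1, repeated in the SAP, sets out the between-arm relapse analysis as Cox regression "with time to relapse as the dependent variable and intervention group as the independent variable". No covariate and no stratification factor is named. Neither document gives a hypothesis, significance level, target hazard ratio or power for this comparison, and its status is plain: "Relapse to tobacco use will be analyzed as an exploratory endpoint".

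The same paragraph allows for more modelling: "Additional multivariable analyses assessing characteristics associated with relapse to tobacco use will be considered". It cautions that "our ability to perform meaningful multivariable analyses will be dependent on the number of subjects that relapse to tobacco use". No covariates are listed for those analyses. Participants who discontinue before one year without having met the relapse criteria are counted as relapsed from the day after their last visit.

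The continuous endpoints are treated differently. The primary ANCOVA compares groups "adjusting for the baseline value of the dependent variable, study site, and any baseline variables found to differ significantly between groups", and the secondary endpoints follow the same pattern, site included.

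Age, gender, cigarettes per day and FTND are named in the phase 1 part of XI.1, as candidate characteristics in a logistic model for abstinence at the end of the cessation program. They are not named for relapse. Time since quitting at randomization varies by design. For self-quitters, "Former smokers will be eligible if they have quit smoking in the past two to six weeks" (VII.E.6); program quitters arrive after a final session about three weeks after quitting. VII.E.2 describes 1:1:1 allocation by sequential sealed envelopes and mentions no stratification.

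**The concern.** The plan accepts the case for baseline adjustment elsewhere: XI.2 prefers ANCOVA partly because it usually has more power. It does not say why relapse is handled differently.

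The relapse comparison also matters more than its label suggests. It is the only planned between-arm test of whether the programs help or hinder abstinence, and the background (I.6, section A.3) reports the argument that weight control can detract from quitting. Relapse also decides who enters the primary analysis, so a difference by arm bears on how the blood pressure and weight results are read.

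In a Cox model, leaving out prognostic covariates places a non-null hazard ratio nearer 1 than the covariate-conditional value, even when the arms are balanced, and some power goes with it. Few events are expected, so the question is how much could be recovered from data already in hand.

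**Working it through.** **1. Event count (Protocol XI.2, Anticipated Attrition).**
- Randomized: 1267 × 0.45 = 570.15, stated as 570, or 190 per arm.
- Discontinue: 570 × 0.10 = 57.
- Relapse: (570 − 57) × 0.15 = 76.95, stated as 78.
- Remaining: 570 − 57 − 78 = 435, as stated.
- Events under the plan's rule: 57 + 78 = 135 (23.7% of 570), of which 57/135 = 42% are imputed. Per pairwise comparison: 135 × 2/3 = 90.

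**2. Power of the model as written.** The plan gives no figure to reproduce. Schoenfeld's formula for equal arms is power = Φ(√d × |ln HR|/2 − z).
- Assumed HR 0.60, d = 90, two-sided 0.05: √90/2 × 0.511 = 2.42; 2.42 − 1.96 = 0.46; power 68%.
- Assumed HR 0.70: 39%.
- At two-sided 0.025: 57% and 29%.

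**3. Gain from adjustment when all 135 events are true, covariate-driven relapses.** The simulations assumed three sites, HR 0.60 and two-sided 0.05. SD is the assumed standard deviation of the log hazard explained by the baseline variables; the documents give no value. Setting A has front-loaded Weibull relapse times (shape 0.6), with FTND, cigarettes per day, age, sex, 20% self-quit entry and site (2000 trials per row). Setting B has a constant hazard, four covariates, and site carrying 30% of the prognostic variance (1500 trials per row).

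| Setting | SD | Power, unadjusted | Power, adjusted | Gain (points) | HR, unadjusted / adjusted |
|---|---|---|---|---|---|
| A | 0.3 | 69% | 70% | 1 | not tabulated |
| A | 0.5 | 66% | 69% | 3 | not tabulated |
| A | 0.8 | 58% | 67% | 9 | 0.63 / 0.60 |
| B | 0.25 | 67.9% | 67.9% | 0 | 0.605 / 0.600 |
| B | 0.5 | 64.5% | 67.4% | 2.9 | 0.612 / 0.597 |
| B | 0.75 | 62.1% | 69.7% | 7.6 | 0.625 / 0.598 |
| B | 1.0 | 53.8% | 66.9% | 13.1 | 0.647 / 0.601 |

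Further runs with the same targets gave 0-4 points for weak to moderate covariates and 7-9 for strong ones. Stratifying by site alone added 1 point or less.

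**4. Gain when dropouts are unrelated to arm and covariates.** Here 10% drop out at uniform times and count as events, with about 135 events in all.

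| SD | Power, unadjusted | Power, adjusted | Gain (points) |
|---|---|---|---|
| 0.3 | 27% | 28% | 1 |
| 0.5 | 25% | 27% | 2 |
| 0.8 | 25% | 27% | 2 |
| 0.5 (setting B) | 34.4% | 35.1% | 0.7 |
| 1.0 (setting B) | 29.5% | 34.9% | 5.4 |

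The hazard ratio is then about 0.73-0.75 unadjusted and 0.72-0.74 adjusted. If dropout depends on arm and covariates, the gain lies between steps 3 and 4.

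**5. Under no effect (HR 1.0).** In setting B both models centre on 1.00-1.01 and reject in 4.5% to 6.4% of trials (simulation error about 0.6 points). Setting A gave about 4-6%.

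**6. Can the data carry the model?** Two arm terms plus five covariates make seven coefficients, since stratifying by site adds none: 135/7 = 19 events per coefficient, or 78/7 = 11 if only actual relapses are counted.

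**The case against.** The case for leaving the model alone is strong. The endpoint is exploratory and carries no power claim. No site-stratified allocation is described that would oblige site in the model. For asking whether arms differ in who reaches the primary analysis, the marginal relapse difference is the relevant quantity. The plan already foresees multivariable work, does not say that arm would be excluded from it, and gives a reason for restraint. Data collection is complete (Protocol I.4 and VII.A.4), so a richer model would be chosen after the data exist. The counting of dropouts as relapses dilutes the comparison more than the missing covariates do: in setting B at SD 0.5 it takes power from about 65-67% to about 34-35%, with or without adjustment.

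Most of this stands and caps the importance of the point. Two parts do not dispose of it. The additional analyses are only to be considered, name no covariates and look for characteristics associated with relapse, so nothing commits to an adjusted arm comparison. And the marginal question is still answered if the unadjusted model is reported alongside.

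A reader might infer that the plan lists its own predictors of relapse and then ignores them. It does not: the four characteristics belong to the phase 1 abstinence model, which self-quitters skip, and using them for relapse is a reasonable borrowing. Time since quitting is likewise named nowhere as a predictor.

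**Conclusion.** A small improvement is available; the planned analysis is not wrong. The relapse model is the one between-arm model that omits site, without explanation. At an assumed hazard ratio of 0.60 and two-sided 0.05, adjustment is worth about 0-4 power points for weak to moderate covariates and up to about 9 at SD 0.8. It is worth about 0-2 points over that range if the imputed dropouts are unrelated to arm and covariates. Only an extreme SD of 1.0 gives more (13 and 5 points). Covariate strength is an assumption throughout.

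A reader might infer that the unadjusted hazard ratio is biased, or the test invalid, because it sits nearer 1. The documents and the calculation do not support that. The shift is non-collapsibility: the unadjusted and adjusted hazard ratios are different valid quantities, they agree when there is no effect, and the false-positive rate stays near nominal. Nor would adjustment rescue the test: with 90 pairwise events, power is modest whichever model is used.

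**What to change.** In Protocol XI.1 and the matching SAP paragraph, specify a Cox model stratified by study site, with intervention group and a fixed list of baseline covariates: FTND, cigarettes per day, age, gender, and either entry route (self-quit or cessation program) or days since quitting at randomization. Say that the first four are taken from the phase 1 model. Define cigarettes per day and FTND as before quitting, so that they mean the same for self-quitters.

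Report BPC versus UL and WGP versus UL hazard ratios with 95% CIs, beside the unadjusted (marginal) ones. If relapse results by arm have already been seen, label the adjusted model post hoc. If the sponsor prefers the unadjusted model, one sentence saying that the marginal effect is intended, and why site is omitted only here, would settle the inconsistency.

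The cost is a sentence or two of SAP text and no new data collection. The adjusted hazard ratio is conditional on the covariates, so it must not be read as the marginal one. If only the 78 actual relapses are counted, about 11 events per coefficient is a reason to keep the list short.

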## **XI.2**

### ***Provide the rationale or power analysis to support the number of subjects proposed to complete this study.***

This study is a multi-site, randomized clinical trial, with study sites in Iowa City, IA, Rochester, MN, and Memphis, TN. The sample size calculations provided below reflect the target number of participants for the entire trial, across each of the three sites. Only subjects that meet criteria for tobacco abstinence at the end of the 4-week smoking cessation phase will be eligible for randomization, and of these participants, only those that meet criteria for prolonged abstinence through 1-year follow-up will be included in the primary analysis. Because methodological factors such as abstinence criteria and length of follow-up can have a significant impact on the primary endpoints, we consulted the extant literature and chose only studies that were fairly similar to the proposed project to obtain estimates for sample-size planning. The majority of these studies present data as change from baseline. For this reason, sample-size calculations for the present investigation are based on an analysis of change scores. However, an alternative to analyzing change scores is to analyze follow-up data using an analysis of covariance model with the baseline value included as a covariate. In addition to adjusting each subject's follow-up score for his or her baseline score, the analysis of covariance approach has the advantage of being unaffected by baseline differences. This approach also typically has greater statistical power to detect a treatment effect than analyzing change scores (Vickers et al. 2001). Therefore, sample-size requirements based on an analysis of change scores will provide similar or greater statistical power for analyses that are performed using an ANCOVA approach.

### **Primary Endpoint: Blood Pressure**

For this endpoint sample-size requirements were determined based on preliminary data from the TONE trial. In this trial the mean change from baseline for the combined Weight Loss plus Sodium Restriction intervention was observed to be -5.3 mmHg (SPB) and -3.4 mmHg (DBP). Effect sizes of similar magnitude have been observed in other studies evaluating lifestyle modification interventions for controlling blood pressure (e.g., Blumenthal et al., 2000; PREMIER Collaborative Research Group, 2003; Singh et al., 1995; Wassertheil-Smoller et al., 1992). From the TONE trial, the pooled estimate of the standard deviation of SBP change from baseline was approximately 14.5 mmHg for SPB and 9.4 mmHg for DBP. Based on these assumed standard deviations, Table 4 lists the sample-size required to provide statistical power of 80% to detect a range of differences between groups with respect to mean BP change from baseline using a two-tailed, alpha=0.025 level test. As can be seen from Table 4, an effective sample-size of 145 per group is required to provide statistical power of approximately 80% to detect

differences between groups consistent with the magnitude of effect observed for the Weight Loss plus Sodium Restriction intervention from the TONE trial.

Table 4. Sample-size for Detecting Difference in Blood Pressure Change from Baseline  
Sample-size requirements for SBP Sample-size requirements for DBP

Difference Between Groups (mmHg)	Standard Deviation (mmHg)	Sample Size	Required per group*	Difference Between Groups (mmHg)	Standard Deviation (mmHg)	Sample Size	Required per group*
5.1	14.5	155	3.1	9.4	176		
5.2	14.5	149	3.2	9.4	166		
5.3†	14.5	144	3.3	9.4	156		
5.4	14.5	139	3.4†	9.4	147		
5.5	14.5	134	3.5	9.4	139		

\* Sample-size required to provide statistical power of 80% using a two-sided, alpha=0.025 level test.

† A difference of this magnitude is consistent with the effect observed for the Weight Loss plus Sodium Restriction intervention from the TONE trial.

#### Primary Endpoint: Body Weight

We identified 5 smoking cessation studies that had weight change data (mean $\pm$ SD) presented for subjects that met continuous abstinence criteria at 1-year follow-up. For those that met criteria for continuous abstinence, the observed weight change from baseline to 1-year follow-up in these studies was 6.2 $\pm$ 5.1 kg (N=20; Dale et al., 1998), 5.9 $\pm$ 7.3 kg (N=17; Gritz et al. 1990), 4.5 $\pm$ 2.9 kg (N=35; Hjalmarson et al. 1997), 5.9 $\pm$ 3.8 kg (N=51; Klesges et al., 1997) and 4.8 $\pm$ 3.9 kg (N=88; Pirie et al., 1992). From these 5 studies, the pooled estimate of the standard deviation of weight change from baseline to 1-year is 4.2 kg. In order to be conservative, for sample-size planning of the current investigation the standard deviation of weight change from baseline to 1-year is assumed to be 5.0 kg. Based on this assumption, Table 5 provides the sample-size required to provide statistical power of 80% to detect a range of differences between groups with respect to mean weight change from baseline to 1-year.

Table 5. Sample-size for Detecting Difference in Body Weight Change from Baseline

Difference between groups (kg)	Standard Deviation (kg)
--------------------------------------	----------------------------

Effect Size‡ Sample

Size

Required  
per group\*

2.50 5.0 0.50 78

2.25 5.0 0.45 95

2.00 5.0 0.40 120

1.75 5.0 0.35 157

\* Sample-size required to provide statistical power of 80% using a two-sided, alpha=0.025 level test.

‡Difference between groups divided by the common standard deviation.

In order to be clinically meaningful, we believe that the mean difference between treatment groups should be 2.0 kg or larger. Thus for the body weight endpoint, an effective sample-size of N=120 subjects per group is required to provide statistical power of 80% to detect a clinically relevant difference between groups. An effective sample-size of 145 subjects per group will provide statistical power of 87% (two-sided, alpha=0.025 level test) to detect a mean difference between groups of 2.0 kg.

Secondary Endpoints:

In general, for a continuous endpoint an effective sample-size of N=145 per group will provide statistical power of 80% to detect a difference between group means consistent with an effect size (i.e. difference between groups divided by the common standard deviation) of 0.37. For the secondary endpoints of total energy, dietary fat intake, urinary sodium excretion, and self-reported physical activity, Table 6 provides the minimum difference that can be detected between groups with statistical power of 80% (two-sided, alpha=0.025 level test) using an effective sample-size of N=145 per group. The standard deviation estimates provided in Table 6 are for the distribution of the given endpoint measured at a single time point. The analyses of the 6- and 12-month outcomes will be performed using ANCOVA with the baseline measurement included as a covariate. Since the power analysis presented in Table 6 does not account for the potential reduction in error variance achieved by adjusting for the baseline value, the minimal detectable difference indicated in the table should be considered a conservative estimate. Thus, an effective sample-size of N=145 per group will provide ample statistical power to evaluate these secondary endpoints.

Table 6. Minimum Detectable Difference for Secondary Endpoints

Endpoint Estimated

Standard Deviation Reference for SD Estimate Minimal Detectable Difference\*

Total Energy, kcal/day 426.5 Eck et al. 1996 158 kcal/day

Dietary fat intake, g/day 18.8 Eck et al, 1996 7 g/day

Urinary chloride excretion, mmol/dayb 65 TOHP Research Group, 1992

Whelton et al., 1998 24 mmol/day

Physical activity, kcal/kg/day 1.5 Dunn et al., 1999 0.6 kcal/kg/day

aDifference between group means that can be detected with statistical power of 80% using a two-sided, alpha=0.025 level test with N=145 per group.

bEstimates based on data utilizing urinary sodium excretion.

[figure not shown]
As noted above, the sample size calculations reflect the total number of participants to

be enrolled across the three study sites. The specific enrollment goal for the Iowa City site is 500 participants. We anticipate that we will need to screen approximately 912 individuals in Iowa City to reach the target number of 500 participants enrolled.

